# Targeted Physical Exam

A targeted physical examination must be performed at entry and all subsequent visits, as specified in the SOE. It should include vital signs (temperature, pulse, and respiratory rate, and resting blood pressure) and is to be driven by any previously identified or new signs or symptoms and diagnoses that the participant has experienced since the last visit.

NOTE: Blood pressure will be measured following the current ACTG Standardization of Blood Pressure Measurement SOP.

# Height

Record height (in centimeters) at screening.

# Weight

Record weight (in kilograms) as indicated in section 6.1.

NOTE: Weight should be done with inner clothing and without shoes.

# BMI

BMI will be calculated at screening using standard formula. BMI will not be recorded on the CRF.

A BMI calculator is available at the DMC website (https://www.fstrf.org).

# 12-Lead ECG

An electrocardiogram (ECG) will be performed at screening. ECG results will not be recorded on the CRF.

NOTE: Participant should rest in a supine position for  $\geq$  5 minutes prior to making a recording. The investigator (or qualified designee) should review the ECG traces recorded in real time for gross abnormalities.

#### Signs and Symptoms

At entry, all signs and symptoms, regardless of grade, that occurred within 42 days prior to study entry must be recorded. Post-entry, only signs and symptoms Grade  $\geq$ 3 and all signs and symptoms that led to a change in treatment (excluding indications for RBV dose modification) or that met ICH, EAE, or SAE guidelines, regardless of grade, must be recorded, and are defined by the protocol as reportable events that will require more detailed event reporting.

## Diagnoses

After entry, record any diagnoses targeted for A5348 that are Grade  $\geq$  3 identified by the ACTG criteria for clinical events and other diseases, any diagnosis regardless of grade that led to a change in treatment (excluding indications for RBV dose modification), or any diagnosis that met ICH, EAE, or SAE guidelines.

#### **Concomitant Medications**

Record new or discontinued concomitant prescription and nonprescription medications.

# Study Treatment Modifications

Record all study drug modifications, including initial doses, participant-initiated and/or protocol-mandated modifications, inadvertent and deliberate interruptions at each visit. Record any permanent discontinuation of treatment.

#### Antiretroviral Medications

Record all modifications to antiretroviral medications including initial doses, participant-initiated and/or protocol-mandated modifications, inadvertent and deliberate interruption, and permanent discontinuation.

#### 6.3.7 Laboratory Evaluations

At screening and entry, all laboratory values must be recorded. For post-entry assessments, record all grades of creatinine and creatinine clearance and all other Grade  $\geq$ 3 laboratory values. All laboratory toxicities that led to a change in treatment (excluding indications for RBV dose reduction), regardless of grade, must be recorded.

All Grade 3 or higher laboratory values, any laboratory value that led to a change in treatment (excluding indications for RBV dose modification) or that met ICH, EAE, or SAE guidelines are defined by the protocol as reportable events that will require more detailed event reporting.

The study team should be notified ([contact]) of any new or worsened Grade  $\geq$  2 creatinine values, new or worsened Grade  $\geq$ 2 proteinuria or glucosuria after week 4 of study treatment.

#### **Fasting Instructions**

Fasting is defined as nothing to eat or drink except prescription medications and water for at least 8 hours. Fasting is only required for blood draws with lipid panel and the tenofovir PK evaluation. If participants are in a non-fasting state, they can proceed with non-fasting evaluations and have a fasting lipid evaluation (if indicated) within 7 days of the visit or undergo the tenofovir PK evaluation (if indicated) within 48 hours of the visit.

#### **Hematology**

Hematocrit, hemoglobin (Hgb), platelet count, red blood cell count (RBC), white blood cell count (WBC) with differential (absolute) including lymphocytes, monocytes, neutrophils, eosinophils, basophils, reticulocyte count, absolute neutrophil count (ANC) and MCV.

Hemoglobin A1C: Required at screening only.

#### Blood Chemistries

Sodium, potassium, chloride, bicarbonate/CO2, blood urea nitrogen (BUN), creatinine, glucose, and lipase.

Uric Acid: required at weeks 0, 12, and 24.

#### Liver Function Tests

Total bilirubin, direct bilirubin, indirect bilirubin, albumin, AST (SGOT), ALT (SGPT), alkaline phosphatase.

# Calculated CrCl

Estimated each time that a creatinine level is determined.

To estimate calculated CrCl, use the following method of Cockcroft and Gault:

- For men: [(140 age in years) x (body weight in kg)] ÷ (serum creatinine in mg/dL x 72).
- For women: use the same calculation as for men, then multiply the result by 0.85.

A calculator is available at the DMC website https://www.fstrf.org/ACTG/ccc.html.

## Lipid Panel (fasting)

Low density lipoprotein (LDL), high-density lipoprotein (HDL), triglyceride (TG), and total cholesterol (TC).

# Coagulation Marker

# Urinalysis

Blood, glucose, leukocyte esterase, pH, protein, urobilinogen. Reflex testing to microscopic urinalysis if dipstick result is abnormal. Please note requirement for frequency of urinalysis testing is determined by ARV regimen (PI/r/tenofovir vs. non-PI/r/tenofovir) as outlined in the SOE, section 6.1.

Record all urinalysis results including glucose and protein results on the CRF.

# Urine Spot Protein & Creatinine

Spot protein and creatinine with calculation of protein/creatinine ratio is required at entry. This should be repeated in any participants who develop new proteinuria or glucosuria, an increase from entry glucosuria or proteinuria by  $\geq$  1+ or who develop an increase in creatinine of 0.4 from entry or CrCl < 50 (see section 7.1.3). Urine spot protein and creatinine should be conducted at each study visit through R+4, unless the preceding visit urinalysis demonstrates resolution of proteinuria and/or glucosuria or an increase in creatinine of 0.4 from entry or CrCl < 50 has resolved.

# Pregnancy Test

For women with reproductive potential: a serum  $\beta$ -HCG documenting a negative result will be required at screening and within 48 hours prior to study entry. Serum tests should have a sensitivity of at least 25 mIU/mL.

Once a participant has enrolled with a negative documented serum pregnancy test and begins using two forms of contraceptives to prevent pregnancy, further testing per section 6.1 (during study drug dosing and in post treatment follow-up) can be urine testing. Urine test must have a sensitivity of at least 50 mlU/mL; if positive, must have immediate confirmation with serum  $\beta$ -HCG.

All women of reproductive potential will have a pregnancy test, as indicated in SOE. In the event of a positive urine pregnancy result, participants will be instructed to stop study drugs immediately and return to the clinic as soon as possible for a serum pregnancy test. See section 7.2 for detailed information regarding study management.

#### **Serologies**

HBsAg will be done during screening with results available prior to study entry. HBsAg will not be recorded on the CRF.

#### 6.3.8 Virologic Studies

#### HCV RNA (screening)

The screening HCV RNA must be obtained within 42 days prior to study entry using any FDA-approved test for quantifying HCV RNA at any local laboratory that has a CLIA certification or its equivalent.

#### HCV RNA (on-study evaluations)

At the entry and post-entry visits, HCV RNA quantification will be performed at the designated testing laboratory) as follows:

Serum HCV RNA real-time testing will be collected, processed, and shipped to the designated testing laboratory (see A5348 laboratory processing chart [LPC] for instructions). These results will be reported within 2-3 weeks after specimen receipt.

NOTE: The study team should be notified ([contact]) of detectable HCV RNA after week 4 of study treatment.

#### HCV Genotype

At screening, the HCV genotype and subtype result will be obtained locally from any laboratory that has a CLIA certification or its equivalent. ONLY IF IT IS NOT AVAILABLE LOCALLY should it be done at the designated testing laboratory (see A5348 LPC).

Stored plasma will be collected at the entry visit for additional testing and may be used for HCV genotype testing if confirmation of genotype is requested by the study team.

HCV genotype sample collected at the time of HCV viral failure confirmation will not be performed locally, but should be collected and shipped as per the LPC.

#### **HCV Resistance Testing**

HCV resistance testing will be performed at entry for all participants and repeated at the time of HCV virologic failure confirmation. Resistance testing at the time of virologic failure will be performed real time. Refer to the A5348 LPC for collection, storage and shipping information.

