# 1.3 Secondary Objectives

- 1.3.1 To assess the impact of LDV/SOF and ritonavir-boosted HIV protease inhibitor (PI/r) coadministration on the pharmacokinetics (PK) of tenofovir (TFV).
- 1.3.2 To assess the impact of LDV/SOF and HIV PI/r coadministration on any associated clinical events attributed to elevated tenofovir levels, including renal toxicity (defined as the development of ≥ Grade 2 renal dysfunction or development of new or worsened proteinuria or glucosuria).
- 1.3.3 To assess the proportion of participants who attain SVR4 (i.e., SVR 4 weeks after stopping HCV antiviral therapy) and SVR24 (i.e., SVR 24 weeks after stopping HCV antiviral therapy) in each study arm.
- 1.3.4 To evaluate baseline predictors of SVR12, including cirrhosis, prior treatment response (relapse, partial response, null responder), HCV genotype (GT)-1a vs. 1b, race, and IL-28B status.
- 1.3.5 To evaluate the association between LDV/SOF adherence and SVR12 in both arms.
- 1.3.6 To evaluate the impact of baseline HCV resistance mutations on the SVR12 attained with retreatment with LDV/SOF (+/- RBV).
- 1.3.7 To evaluate emergence of HCV resistance mutations in participants who fail to attain SVR12 with retreatment with LDV/SOF (+/- RBV).

- 1.3.8 To evaluate kinetics of HCV RNA during treatment (weeks 1, 2, 4, 8, 12, and in Arm B, weeks 16, 20, and 24) and 4, 12, and 24 weeks after treatment discontinuation.
- 1.3.9 To assess the influence of LDV/SOF based retreatment on HIV-specific parameters, including maintenance of HIV-1 RNA < 50 copies/mL for participants on antiretrovirals and CD4+ cell count during treatment.
- 1.3.10 To evaluate differences in SVR12 among participants receiving specific antiretroviral (ARV) therapy regimens compared to those taking no ARV on SVR12.
- 1.3.11 To compare the SVR12 proportions, safety, and tolerability in the two arms.

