2.3.1 Clinical efficacy in participants with GT-1 HCV infection and HIV coinfection

The efficacy data for LDV/SOF in GT-1 and 4 HCV infections are derived from the Phase III ION-4 study, which was a multicenter, open-label, single arm study of LDV/SOF for 12 weeks. The trial included HCV treatment-naïve and treatmentexperienced (55%) participants and included 20% of participants with cirrhosis. Participants were required to be on ARVs and have evidence of HIV viral suppression. The allowable ARVs included TDF plus efavirenz (EFV), raltegravir (RAL), or rilpivirine (RPV). Overall, the study population was 82% male, 34% self-reported black race, 24% IL-28B CC genotype, and 98% GT-1 (75% 1a, 23% 1b, 8% GT-4). The overall SVR12 was 96% (96% GT-1 and 100% GT-4). Virologic failures included 10 participants with relapse after end of therapy and 2 participants with breakthrough due to nonadherence. One participant was lost to follow-up after achieving SVR4 although this participant did return for SVR24 visit. There was one death for an unrelated event (infectious endocarditis in IDU). There was no difference in SVR12 for treatment-naïve (95%), treatmentexperienced (97%), cirrhosis (94%), no cirrhosis (96%), treatment-experienced with cirrhosis (98%). In a multivariable analysis only self-reported black race was associated with a lower SVR12 (90%). This association of lower SVR12 and race was not observed in the mono-infected Phase III program. Further investigations to explain this observation in ION-4, including population PK across race, ARV regimen, relapse and a candidate gene study of the CYP2B6 polymorphism, were negative. Deep sequencing was completed on all participants and NS5A

resistant variants (RAV) were identified at baseline in 20% of participants; this did not associate with lower SVR12 (94% with RAVs at baseline vs 96% without). Ten of the 12 virologic failures in the study had RAV at failure, 4 of these were relapsers who had the RAVs at baseline.

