	days prior to entry)			1	2	4 8 12 		12 	16	20	24 	R+4	R+12	R+24	HCV VF Confirmation	HIV-1 VF (	rem.
HCV RNA			``	in ± 3 ys)		(	(Within :	± 7 days	5)		(Within -5 to +7days)	(Within -5 to +14days)	(Within -7 to +14days)	НС	-VIH	άä	
HCV RNA (Real time)		х	х	х	х	х	х	x	x	x	х	x	х	х		х	
Plasma HCV Genotype Test	х													х			
HCV Resistance Testing		х												х			
Stored Plasma for HCV Studies (see section 6.3.8)		x	х	x	x		x			x				х		x	
Plasma HIV-1 RNA (real- time)⁵	х	X 			X 		X 			X 	X 				X 	X 	
Plasma HIV-1 RNA Resistance Testing															х		
CD4+/CD8+	Х	Х					Х			Х						Х	
Stored Whole Blood Sample for Future Genetic Testing		х															
Stored Urine		Х			Х		Х			Х	Х					Х	

						STE	EP 1					STEP 2		L	Ľ							
Evaluations (Within days pl	Screening (Within 42	Entry	On-Treatment (Arms A&B) Week						On-Treatment (Arm B only) Week			Post-Treatment (Arms A&B) (R=Date of Last Dose of Study Treatment) Week			Confirmation	Prem. Tx/Study Discontinuation 						
	to entry)			-	-				1	2	4	8	12 	16	20	24 	R+4	R+12	R+24	HCV VF Confirmation	HIV-1 VF	rem. iscon
			``	in ± 3 ys)		(	Within ±	E 7 days	5)	I	(Within -5 to +7days)	(Within -5 to +14days)	(Within -7 to +14days)	HCV	-VIH	ша						
TFV PK Evaluation (pre-dose, 1hr, 4hr)  (FASTING)		x			x																	
Dried Blood Spots for PK		х	х	х	х	х	х	х	х	х	Х											
IL-28B Genotype		х																				
Pregnancy Prevention Counseling	х	х			х		х				х					х						
Adherence Assessments (4 day recall, pill counts)			х	х	х	х	х	х	x	х												
Study Drug Dispensing		х			х	х	х	х	х													
Medication Diary  (D=distribution, C=collect)		X (D)	X (C/D)	X (C/D)	X (C/D)	X (C/D)	X (C/D)	X (C/D)	X (C/D)	X (C/D)	X (C)											

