## 8.2 Premature Study Discontinuation

- Request by the participant to withdraw.
- Request of the primary care provider if s/he thinks the study is no longer in the best interest of the participant.
- Participant judged by the investigator to be at significant risk of failing to comply with the provisions of the protocol as to cause harm to self or seriously interfere with the validity of the study results.
- At the discretion of the Study Monitoring Committee (SMC), ACTG, institutional review board (IRB), NIAID, Office for Human Research Protections (OHRP), any other government agency as part of their duties, investigator, or industry supporter.
- Initiation of alternate non-study HCV treatment.

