- 9.2.2.4 HCV RNA <LLOQ (either TD or TND) at post-entry scheduled visits, using the visit windows as defined in section 6.
- 9.2.2.5 HIV-1 RNA > 50 copies/mL at all scheduled visits, using the visit windows as defined in section 6.
- 9.2.2.6 Change in CD4+ cell count from study entry at subsequent scheduled visits, using the visit windows as defined in section 6.
- 9.2.3 Exploratory Outcome Measures
  - 9.2.3.1 HCV resistance mutation at study entry. The set of mutations to be considered will be defined prior to analysis based on the latest information.
  - 9.2.3.2 Development of resistance mutation in SVR12 failures.
  - 9.2.3.3 Tenofovir area under the curve (AUC) at baseline (prior to study treatment initiation) and at week 4.
  - 9.2.3.4 SOF and LDV metabolite concentrations.
- 9.3 Randomization and Stratification

The study is randomized to Arm A and Arm B and stratified by the cirrhosis status. Initially, 15 slots will be reserved for participants taking a PI/r and tenofovir regimen across the two study arms. This will be lifted 3 months after the study is open to accrual, so that the accrual progress is not constrained by the PK objective on tenofovir.

The first 15 participants whose ARV regimen contains HIV PI/r plus tenofovir who enroll to the study must be willing to participate in PK sampling (pre-dose, hour 1 and hour 4) at weeks 0 and 4. After 15 such participants have contributed PK samples, participation in the tenofovir PK sampling is optional. Study accrual may conclude with fewer than 15 participants whose ARV regimen contains HIV PI/r plus tenofovir, since the reservation of 15 slots will be lifted 3 months after the study is open to accrual. There is no minimum or maximum for such participants.

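### No plasma for sequencing is scheduled at R+4, R+12 or R+24, so resistance data after relapse rest on a confirmation visit or a formal study-discontinuation visit

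*Protocol*

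**What the plan says.** Protocol section 1.3.7 sets the secondary objective "To evaluate emergence of HCV resistance mutations in participants who fail to attain SVR12" after retreatment. The matching outcome, 9.2.3.2, is exploratory: "Development of resistance mutation in SVR12 failures".

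On specimens, section 6.3.8 states that "HCV resistance testing will be performed at entry for all participants and repeated at the time of HCV virologic failure confirmation". Section 6.3.10 ties stored plasma to the visits marked in section 6.1. It also promises plasma for resistance testing if virologic breakthrough occurs, but does not mention relapse. Section 7.3 places breakthrough among the on-treatment stopping criteria.

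On relapse, section 6.2.4 defines it as HCV RNA below LLOQ at the end of treatment and at or above LLOQ during follow-up. It requires a confirmation sample within two weeks of the first observation. On the HCV RNA assay that would reveal a relapse, section 6.3.8 says: "These results will be reported within 2-3 weeks after specimen receipt".

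On the endpoint, section 9.2.1.1 decides SVR12 on the R+12 window sample closest to target. A missing sample counts as failure unless the results before and after it are both below LLOQ.

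SAP 4.4.3 lists participants in whom a targeted mutation was found in any tested sample, with their SVR12 outcome.

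**The concern.** The objective concerns SVR12 failures, but the specimens needed to address it are not scheduled at the visits where most such failures would first be seen. In the coinfection trial summarised in Protocol section 2.3.1, relapse was the main form of failure: "Virologic failures included 10 participants with relapse after end of therapy and 2 participants with breakthrough due to nonadherence". A relapser's on-treatment plasma cannot show what emerged, because the virus was below LLOQ at the end of treatment. If that person attends R+12, has quantifiable virus and does not come back, the protocol designates no specimen for sequencing.

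The SAP listing makes such a loss hard to see. It contains only participants with a mutation detected, so an SVR12 failure who was never sequenced is absent in the same way as one who was sequenced with no mutation found. With few failures expected, one missing sequence is a large share of the evidence.

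**Working it through.** The plan states no figure on this point, so there is none to reproduce. The check has four parts.

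**1. Schedule of Events rows, aligned to the 16 visit columns**

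| Row | Marked at | R+4, R+12, R+24 |
|---|---|---|
| HCV RNA (real time) | entry, all post-entry visits, HCV VF confirmation, premature discontinuation | marked |
| Stored plasma for HCV studies | entry, weeks 1, 2, 4, 12, 24, HCV VF confirmation, premature discontinuation | blank |
| HCV resistance testing | entry, HCV VF confirmation | blank |

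The post-treatment HCV RNA draw is serum for real-time quantification. The protocol states no sequencing use for it.

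**2. Routes to a post-relapse specimen**

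- Confirmation visit: required by 6.2.4 and 7.3, with both plasma and resistance testing marked.
- Premature study discontinuation visit: plasma is marked, resistance testing is not. It covers only those who formally leave.
- On-treatment plasma: taken before relapse.
- Breakthrough plasma (6.3.10): relapse is not mentioned.
- Neither of the first two visits attended: no designated specimen.

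If confirmation does occur, the time from first quantifiable sample to confirmation sample can reach 21 + 14 = 35 days, excluding shipping.

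**3. Size**

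Inputs: N = 40 planned (Protocol Schema) and N = 7 enrolled (SAP 2.1); SVR12 = 90% (Protocol 9.4.1), so failure rate f = 0.10. The share q of SVR12 failures who attend neither visit is not in the documents; 5%, 20% and 50% are assumed.

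Expected failures = N × f: 40 × 0.10 = 4.0; 7 × 0.10 = 0.7. If failures follow the cited trial, 4 × 10/12 = 3.3 of the planned 4 would be relapses.

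Expected unsequenced failures = N × f × q. Chance of at least one = 1 − (1 − f × q)^N, with participants independent.

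| q | N = 40: expected | N = 40: chance | N = 7: expected | N = 7: chance |
|---|---|---|---|---|
| 5% | 0.2 | 1 − 0.995^40 = 0.18 | 0.035 | 1 − 0.995^7 = 0.03 |
| 20% | 0.8 | 1 − 0.98^40 = 0.55 | 0.14 | 1 − 0.98^7 = 0.13 |
| 50% | 2.0 | 1 − 0.95^40 = 0.87 | 0.35 | 1 − 0.95^7 = 0.30 |

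At 70% SVR12, the level section 9.4.1 uses as its benchmark of acceptability, f = 0.30. The same formula gives 0.45, 0.92 and 1.00 at N = 40, and 0.10, 0.35 and 0.68 at N = 7. Every SVR12 failure is treated here as a relapse seen at an attended visit, so these figures err on the high side.

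**4. Visits that could still benefit**

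Accrual closed on 21 July 2016, and SAP Version 2.0 cites a call on 6 January 2017. On the nominal schedule, an Arm A participant entering on the last day ends treatment after 84 days (13 October 2016), reaches R+4 on 10 November 2016 and R+12 on 5 January 2017. An Arm B participant entering that day ends treatment after 168 days (5 January 2017), reaches R+4 on 2 February 2017 and R+12 on 30 March 2017. Apart from visit windows and delays, only some Arm B post-treatment visits and Arm A R+24 visits could then remain.

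**The case against.** The strongest reply is that confirmation is mandatory. Sections 6.2.4 and 7.3 require it, and section 9.2.1.1 only derives the endpoint without waiving it. A gap arises only when a participant departs from the protocol. This stands, and it limits the point to non-attenders.

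A reader might infer that emergent-resistance data depend wholly on the confirmation visit. They do not. The discontinuation visit also stores plasma, and section 6.2.5 requires that evaluation before a participant is taken off study.

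A reader might also infer that early outside retreatment is a main route of loss. Section 8.2 lists "Initiation of alternate non-study HCV treatment" as a reason for premature study discontinuation, so by protocol it leads to that plasma draw.

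It is equally tempting to say that some failures will miss confirmation, or that about three in four sequences would be lost. No attendance rate is given, and 10/12 is the share of virologic failures that were relapses in another trial, not a share lost.

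Other limits stand as well:

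- A missed R+12 visit is not rescued by an aliquot scheduled at that visit.
- A relapse first seen at R+24 after a result below LLOQ at R+12 is not an SVR12 failure, so it falls outside 1.3.7.
- Nothing in the documents shows that a delay of up to 35 days loses emergent mutations.
- Separating relapse from reinfection on study is not a stated objective, and genotype is collected at confirmation.
- Collection and storage details are deferred to the laboratory processing chart, so retention of residual serum cannot be judged.
- The outcome is exploratory and the SAP output is a listing, so no estimate is biased. SAP 4.3.1 already reports reasons for non-SVR.

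What survives is the relapser who attends R+4 or R+12, has quantifiable virus, and then attends neither further visit. The SAP listing does not make that case visible.

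**Conclusion.** The gap is real and narrow. Post-relapse sequence data for 1.3.7 and 9.2.3.2 rest on two visits, and a relapser who attends neither has no designated specimen. Its size depends on an assumed non-attendance of 5% to 50%, on 90% SVR12, and on independence between participants. As designed, the chance of at least one such failure was appreciable over most of that range. With 7 enrolled, at most about a third of one participant is expected to be affected, and many of the relevant visits had nominally passed when SAP Version 2.0 was written. This is a cheap improvement of low practical impact at the current size, and it does not bear on the SVR12 analysis.

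**What to change.** 1. In the stored-plasma row of the Schedule of Events, add R+4 and R+12 for any such visits still to come. R+24 is useful but secondary.
2. In section 6.3.8, state that if a post-treatment HCV RNA is at or above LLOQ and no confirmation sample is obtained, resistance testing is run on the plasma stored at that visit.
3. In SAP 4.4.3, list every SVR12 failure, with columns showing whether a post-failure sequence exists, from which visit, and the result. An unsequenced failure then cannot be read as one without mutations.

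Items 1 and 2 cost a small extra blood volume at visits where blood is already drawn, storage, occasional sequencing and a letter of amendment. Item 3 needs only a SAP edit and is worth making even if no post-treatment visits remain.
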